### **Deviations and Unanticipated Problems**

**Deviation** - A deviation is a divergence from a specific element of a protocol that occurred without prior IRB approval. Investigators may deviate from the protocol to eliminate immediate hazard(s) for the protection, safety, and well-being of the study subjects without prior IRB approval. For any such deviation, the PI will notify the COH DSMC and IRB within 5 calendar days of its occurrence via [iRIS](#) in accordance with the [Clinical Research Protocol Deviation policy](#) [policy effective date: 11/07/11].

## **Single Subject Exception (SSE)**

An SSE is a planned deviation, meaning that it involves circumstances in which the specific procedures called for in a protocol are not in the best interests of a specific patient. It is a deviation that is anticipated and receives prior approval by the PI and the IRB. The SSE must be submitted as a “Single Subject Exception Amendment Request” via [iRIS](#) in accordance with IRB guidelines and the [Clinical Research Protocol Deviation policy](#) [policy effective date: 11/07/11]. An IRB approved SSE does not need to be submitted as a deviation to the DSMC.

**Unanticipated Problem (UP)** – Any incident, experience, or outcome that meets all three of the following criteria:

1. Unexpected (in terms of nature, severity, or frequency) given the following: a) the research procedures described in the protocol-related documents such as the IRB approved research protocol, informed consent document or Investigator Brochure (IB); and b) the characteristics of the subject population being studied; **AND**
2. Related or possibly related to participation in the research (possibly related means there is a reasonable possibility that the incident, experience, or outcomes may have been caused by the drugs, devices or procedures involved in the research); **AND**
3. Suggests that the research places subjects or others at greater risk of harm (including physical, psychological, economic, or social harm) than previously known or recognized.

Any UP that occurs during study conduct will be reported to the DSMC and IRB in accordance with the [City of Hope’s Institutional policy](#) [policy effective date: 05/14/14] using [iRIS](#).

---

## **8.0 Agent Information and Risks**

### **8.1 Interleukin-2 (IL-2)**

#### **8.1.1 Description**

**Chemical name:** Recombinant human Interleukin 2 /IL-2 (Proleukin®)

**Classification:** Cytokine

**Mechanism of action:** Lymphocyte Growth factor.

IL-2 primarily promotes effector T cell responses in vivo, and is now known to be a cytokine critical for the development, expansion, survival and peripheral activity of regulatory T cells (Treg).

#### **8.1.2 Toxicology**

IL-2 administration by the SC route has been evaluated in several multiple-dose studies in rats for up to 13 weeks of daily. They confirmed that the SC high-dose toxicity profile in rats was comparable to the high-dose toxicity profile after IV administration. IL-2-related findings included lymphocytosis, eosinophilia, slight anemia, extramedullary hematopoiesis, lymphoid hyperplasia, hepatomegaly and splenomegaly. Infiltrative and proliferative changes were seen in many organs, including liver, lung, lymph nodes, kidney, spleen and bone marrow.

In summary, the toxicity of IL-2 in animals has been shown to be dose- and duration-related, with all toxic effects being directly or secondarily related to IL-2 pharmacological activity. In animal species, treatment-related effects were fully or partially reversible after a treatment-free period of 2-4 weeks. Findings were comparable after repeated IV or SC administration of IL-2. The severity of target organ toxicity has been correlated with the extent of inflammatory cell infiltration into these organs. Biological effects in animals were generally similar to effects reported in clinical trials. However, these MTD studies relate to the high-dose IL-2 used for treatment of metastatic RCC and melanoma, rather than the low-dose IL-2 proposed for in-vivo Treg enhancement in our study. Additional information regarding the nonclinical pharmacology and toxicology of IL-2 may be found in the full prescribing information.

Low-dose IL-2, administered s.c. for extended periods, has been evaluated in patients with HIV infection. In one study of ultra-low-dose in 11 patients with HIV infection, s.c. IL-2 in doses ranging from 0.4-1.4 million Units /m^2/day, s.c. IL-2 was well absorbed after administration, with a Tmax of 4.4 ± 1.5 hours and was undetectable 24 hours after injection.

Low-dose IL-2 has also been safely used in patients with hematologic malignancy after allogeneic HSCT. Rizzieri et al. reported use of IL-2 starting six weeks post Allo-HCT using T depleted grafts at dose of 1 million units/m^2. Patients were treated on a four-weeks-on and 2-weeks-off schedule for up to a year to determine if relapse rates were reduced in the setting of non-myeloablative HCT with immune modulation by post HCT IL-2. Fatigue was the main side effect noted with this dose of IL-2. Seven of the 8 patients completed at least 2 cycles, though 1 patient withdrew after cycle 1 and 3 patients withdrew after 2 cycles (3 months) due to excessive fatigue, and 1 withdrew after 6 cycles due to persistent skin GVHD. One further patient had early progressive disease (relapse) after 2 cycles of therapy. Though only 2 completed the maximum of 8 cycles of therapy over the 1 year period, only 1 patient was unable to tolerate at least 2 cycles (3 months) of therapy. Both patients with a mismatched donor tolerated only 2 cycles of therapy, though 1 remains in a long term remission.

In one study by Soiffer et al., IL-2 was administered by continuous IV infusion to 13 patients with T-cell depleted (TCD) allogeneic HSCT (n=6) and (n=7) patients post autologous HCT. IL-2 was infused at a dose of 0.2 million IU/m^2/day by hickman catheter for 90 days using a portable pump beginning at a median of 85 days. The majority of patients who received prolonged continuous infusion of low-dose rIL-2 post-BMT tolerated treatment without severe toxicities. No patient developed pulmonary capillary leak syndrome, severe hypotension requiring pressors, oliguria, azotemia, or hyperbilirubinemia during the 90-day course. Two individuals, both recipients of T-depleted allogeneic marrow, developed fever (38.5° C), nausea, and vomiting within 72 hours of initiation of IL-2. When therapy was interrupted, symptoms resolved within 3 days. Fatigue was the most common complaint and occurred in six patients-it did not interfere with daily activities. A 5% to 7% gain in body weight was documented in 5 of 13 individuals, all of whom had peripheral edema. Five patients developed a nonproductive cough; however, only one (with preexisting emphysema) complained of subjective dyspnea on exertion. Cough abated within 1 week of completing treatment in all patients. Localized rashes occurred in six patients, but were transient and resolved before discontinuing IL-2. Immunophenotypic analysis of PBMC was performed routinely while patients received IL-2. The fraction of lymphocytes expressing the NK cell-associated antigen NKH1 (CD56) increased steadily over time, rising from a median of 15% initially to 70% within 8 weeks of initiating IL-2 therapy and there was a concomitant increase in the absolute number of NK cells as well.

In DFCI 07-083, the safety and immunologic activity of low-dose interleukin-2 in patients with active cGVHD was assessed. The primary objective of this study was to determine the MTD and toxicity profile of an 8 week course of IL-2 in patients with chronic GVHD who had an inadequate response to steroids. Eligibility included patients with cGVHD requiring systemic therapy that had not responded to at least 0.25 mg/kg prednisone for a 4 week period, absence of infection, and stable doses of immune suppression for 4 weeks. The study has a Phase 1 dose escalation design with 3 dose levels (0.3, 1, and 3 x 10^6 IU/m^2/day for 56 days). 29 patients were accrued on protocol; with 28 subjects evaluable for toxicity and 23 evaluable for response. The interval between onset of chronic GVHD and initiation of IL-2 was 803

days (range, 117-2624). Patients were on a median of 3 concurrent agents (range, 1-3) for cGVHD. Skin and fascia were primary sites of involvement, but lung, liver, oral, and ocular sites were involved as well. Dose-level-C ( $3 \times 10^6$  IU/m^2/day) was infeasible due to persistent constitutional side-effects requiring dose reduction. Dose-level-B ( $1 \times 10^6$  IU/m^2/day) was determined to be maximum-tolerated-dose in this patient population. 2 patients developed dose-limiting-toxicity (thrombotic microangiopathy). 3 had CTC grade  $\geq 3$  infections unrelated to IL-2. None experienced GVHD flare. There was no malignant disease relapse. 12/23 patients had major responses. These results suggest that low-dose IL-2 can be administered safely in patients with active inflammation of chronic GVHD.

### 8.1.3 Expected Toxicities with IL-2

A list of the adverse events and potential risks associated with the agents administered in this study appear below and will determine whether dose delays and modifications will be made or whether the event requires expedited reporting in addition to routine reporting.

*Local Reactions (expected in 10% patients):* Patients receiving daily SC low-dose IL-2 have been reported to develop injection site reactions, typically focal erythema that resolved in a few days; and induration that resolved after 2-3 weeks. Dose interruptions may occasionally be required in patients with more marked induration (CTCAE 4.0; Grade 3). Lengthy dose interruptions may result in patients being unevaluable for response (Section 6.1)

*Constitutional symptoms (expected in 5% patients):* In the allo-HCT setting, some patients on low-dose IL-2 developed fever, nausea and arthralgia within 72 hours of starting IL-2. Interruption of therapy for 3 days is recommended if symptoms reported are severe and affecting ADL's i.e. Fatigue  $\geq$  Grade 3 per CTCAE 4.0 criteria. If symptoms of fatigue resolve in 72 hours; IL-2 may be restarted at 50% of prior dose. If however symptoms of fatigue persist and patient is unwilling to continue therapy on protocol, they will be removed from study. Secondary/reversible causes of fatigue, such as sepsis, hypotension, hypothyroidism will be ruled out prior to attributing this to IL-2.

*Thyroid dysfunction (expected in 5% patients):* Thyroid function test abnormalities were noted in some allo-HCT patients on low-dose IL-2. Only one patient however developed clinical hypothyroidism necessitating therapy while on IL-2. After cessation of IL-2, thyroid function returned to normal. Hence, a thyroid panel (TSH, T4, free T4) levels will be checked at study entry and week 12 while on study. Patients with evidence for hypothyroidism will be worked up (antimicrosomal, antithyroglobulin antibodies) and given replacement thyroxine as clinically indicated.

*Hematologic (expected in 5% patients):* Early post-HSCT, low-dose IL-2 caused an initial decrease in the absolute lymphocyte count in patients after 1 week of therapy. Thereafter, with continued infusion, a steady increase in lymphocyte count occurred in all patients.

- Low dose IL-2 also caused an initial increase in eosinophil counts (peak at 3 weeks) followed by a gradual decline.
- The platelet count decreased by >20% in some allo-HCT patients on low-dose IL-2. This decrease was noted within the first 2 weeks on IL-2, and continued treatment was not associated with further declines in platelet count. No patients had >40% decline in platelet counts, and none required platelet transfusions or had bleeding episodes.
- No changes in monocyte or neutrophil counts were observed. No significant impact of low-dose IL-2 on hemoglobin levels or reticulocyte counts was noted.

*Thrombotic Microangiopathy (TMA) (expected in 7% patients):* Koreth et al. reported 2 patients on daily SC low-dose IL-2 who developed SAE of thrombotic microangiopathy (thrombocytopenia, microangiopathic hemolytic anemia with schistocytosis, renal dysfunction) that was thought possibly related to IL-2. TMA is also a known complication of calcineurin-inhibitor and of sirolimus (both of which both the patients were on). One of the patients has required long-term hemodialysis for management of renal dysfunction.

#### 8.1.4 Pharmacology – Handling, Storage, Dispensing and Disposal

##### 8.1.4.1 *Form:*

Recombinant human IL-2 (Proleukin®) is supplied as a sterile, white to off-white, lyophilized cake in single-use vials containing 22 MIU of aldesleukin intended for intravenous (IV) or subcutaneous (SC) administration. Store vials of lyophilized IL-2 in a refrigerator at 2-8°C (36-46°F). Do not use beyond the expiration date printed on the label.

For the 22 million international unit (MIU) vial, when reconstituted with 1.2 mL Sterile Water for Injection (SWFI), each mL contains 18 MIU (1.1mg) IL-2, 50 mg mannitol and ~180 mcg sodium dodecyl sulphate, buffered with ~170 mcg sodium phosphate monobasic and 890 mcg sodium phosphate dibasic to a pH of 7.5 (range: 7.2-7.8)

##### 8.1.4.2 *Storage and Stability:*

Store vials of lyophilized IL-2 in a refrigerator at 2-8°C (36-46°F). Do not use beyond the expiration date printed on the label. Vials should be entered only once for reconstitution to minimize the chances of contamination. If not used immediately, in-use storage times should normally not be longer than 24 hours at 2-8°C, unless reconstitution has been performed under controlled and validated aseptic conditions in a laminar airflow hood.

Data support stability and sterility of reconstituted diluted IL-2 preparations (reconstituted with SWFI and further diluted with D5W); and the stability and sterility of product reconstituted with SWFI but not further diluted, for up to 14 days at 2-8°C (36-46°F) when single-use syringes for daily use are prepared by qualified health-care professionals under aseptic conditions (per Proleukin® Investigator's Brochure (Chiron Corporation, 10 Sep 2003, pp113). IL-2 should be reconstituted with sterile water for injection (SWFI) plus D5W. Reconstitution or dilution with Bacteriostatic Water for Injection or 0.9% Sodium Chloride for Injection should be avoided due to increased aggregates.

Therefore, reconstitution and dilution of lyophilized IL-2 is to be performed under controlled and validated aseptic conditions in a laminar flow hood per COH pharmacy policy and procedure manual. The dose or doses thus prepared and stored at 2-8°C (36-46°F) need to be used within 14 days.

##### 8.1.4.3 *Compatibility:*

IL-2 is not given IV, hence compatibility issues with other concomitant IV drugs are not applicable. IL-2 has been used in combination with steroids, mycophenolate mofetil, calcineurin inhibitors, sirolimus and imatinib without any adverse effects.

##### 8.1.4.4 *Handling*

The single-daily-use syringes containing reconstituted and diluted solutions should be stored in a refrigerator at 2-8°C. DO NOT FREEZE. The product should be inspected visually for particulate matter or discoloration and brought to room temperature before administration.

##### 8.1.4.5 *Preparation:*

IL-2 will be reconstituted in 1 ml Becton Dickinson single use syringes. All IL-2 syringes for daily SC outpatient use should be prepared in the pharmacy at the same time, after diluting the 22 MIU IL-2 vial with 1.2 ml SWFI and 4.8 ml D5W (final IL-2 concentration=3.6 MIU/mL), and any remaining product

should be immediately discarded. During reconstitution the SWFI should be directed at the sides of the vial to avoid foaming, and the contents of the vial should be gently swirled. THE VIAL SHOULD NOT BE SHAKEN.

*8.1.4.6 Administration:*

After reconstitution, an up to 2-week IL-2 supply will be provided in single-use syringes (in a cool-pack if necessary), for home refrigerator storage at 2-8 C. One single-use syringe will be used each day during home SC self-administration, and discarded in the sharps containers provided. Participants will be instructed to rotate injection sites, if feasible.

*8.1.4.7 Accountability:*

The investigator, or a responsible party designated by the investigator, must maintain a careful record of the inventory and disposition of the agent (investigational or free of charge) using the NCI Drug Accountability Record or another comparable drug accountability form.

*8.1.4.8 Destruction and Return:*

At the end of the study, unused supplies of IL-2 should be destroyed according to institutional policies. Destruction will be documented in the Drug Accountability Record Form.

*Hematoma:* Leakage of blood from vein into the surrounding tissues causes bruising. This could occur with any needle puncture into a vein and could produce pain or even limit the full use of the affected arm for a few days. Such a leak can occur at any point or after the treatment. Pressure bandage applied after treatments are intended to limit the occurrence of this complication.

*Loss of blood:* Leakage/breakage of the plastic tubing rarely occurs but may develop during the treatment. This would result in potential contamination of the portion of blood in the cell separator. As a safety measure, this blood will not be returned to the patient.

## **9.0 Correlative/Special Studies**

---

### **9.1 Immune Correlative Studies:**

Chronic GVHD is associated with a deficiency of T-reg, NK cells and naive CD8+ T cells. Studies support increased pro-inflammatory cytokines in chronic GVHD cases, including TNF- $\alpha$ , IL-6, IL-1 $\beta$ , IL-8, soluble alpha chain of the IL-2 receptor shed by activated T cells (sIL-2R) and IL-1R $\alpha$ , among others and decrease in anti-inflammatory cytokines such as IL-10. Early-onset chronic GVHD had increased soluble B cell activating factor (sBAFF), anti-dsDNA, sIL-2R $\alpha$  and sCD13. Late-onset chronic GVHD cases had increased sBAFF and anti-dsDNA. Additionally, early onset chronic GVHD demonstrates decreased IFN- $\gamma$  and IL-2, while late-onset chronic GVHD had decreased IL-4, IL-2 and FOXP3. CRP and C3 and C4 complement levels are also elevated in cGVHD.

The primary immunologic endpoint is a fold-increase in T-reg and the T-reg/-Tcon ratio at 3 months of (ECP+IL2) therapy. Protocol-specified immunophenotypic analyses will be performed at baseline and at 3, 7, 9 & 12 weeks during treatment with ECP +IL-2 and 4 weeks after discontinuation of combination therapy (week 16 for those who complete treatment).

The following analysis will be performed:

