There are few randomized controlled trials for use of ECP in cGVHD and most physicians use clinical experience and patient response to formulate institutional guidelines regarding frequency and duration of ECP usage. Based on in-house physician expertise in the COH Department of Transfusion Medicine, who have performed thousands of ECP procedures, we utilize an ECP schedule of: 2 procedures per week for the first month, followed by 2 procedures every 2 weeks for the next 3 months. For the purpose of this trial, we will continue using this regimen based on extensive local experience.

In conclusion, ECP is an important tool for use of therapy in steroid refractory and steroid dependent cGVHD with overall response rates of approximately 30% and partial responses in a majority of patients

treated. Responses depend on site of involvement with better outcomes in skin, hepatic, oral and ocular involvement. Patients presenting with de novo cGVHD, without history of preceding aGVHD also tend to respond better. Treatment responses improve with duration of therapy and most patients can gradually be tapered off ECP in 4-6 months. Treatment outcomes are better if instituted early in the course of cGVHD. However, enthusiasm for ECP in patients with cGVHD has to be tempered by the fact that large randomized controlled trials are lacking and few prospective trials have been done in this hard to treat patient population. Moreover, few patients achieve complete remissions, although a majority derives clinical benefit after ECP therapy from disease stabilization and partials responses. In most trials, ECP also helps patients to reduce the amount of steroid use. We believe that the complete and partial response rates should be improved upon by combining this therapy with other agents such as low dose IL-2.

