### 2.1.4 Rationale for combination of ECP and IL2 for cGVHD

As demonstrated in the literature reviewed above, cGVHD is a multisystem disorder caused by impaired immune reconstitution post Allo-HCT with allorecative T cells from donor causing immune mediated organ damage in skin, liver and GI tract. This condition is characterized by relative paucity of T reg

compared to Tcons leading to decline in Treg:Tcon ratio. Normalization of Treg:Tcon ratio is associated with objective clinical improvement in signs and symptoms of cGVHD. ECP has been used successfully in patients with chronic steroid-refractory GVHD, with complete responses noted in 30% of patients. Improvement in cGVHD symptoms in responding patients has been co-related with a concurrent increment in Tregs. Hence ECP is a proven treatment modality in patients with steroid refractory cGVHD and responding patients demonstrate a normalization of Treg:Tcon ratio.

More recently, IL-2 has shown promising results in a phase I dose escalation trial, wherein it was shown to be safe at a dose level of  $1 \times 10^6$  units/m^2 when used in patients with steroid refractory cGVHD. Clinical benefit (partial response and stable disease) 52% of patients on low dose IL-2 therapy. In this trial no complete responses were noted. Co-relative studies demonstrated that patients with cGVHD responding clinically had a significant expansion of T reg pool while on therapy, with responses noted as early as 2 weeks into therapy. This expansion of T regs persisted during the remaining duration of therapy and declined to baseline levels 4 weeks after discontinuation of subcutaneous IL-2. Relapse of cGVHD is noted after discontinuation of IL-2 therapy and this may be related to gradual decline in T regs after stopping IL-2 therapy.

In this phase II prospective trial in patients with steroid-refractory cGVHD, we propose to combine low dose IL-2 with ECP, based on the following:

- A. We hypothesize that combination therapy with IL-2 and ECP will lead to a greater increase in Tregs compared to historic controls when either modality was alone. This is because both ECP and IL-2 boost regulatory T cells (Tregs). The effect of combining ECP and IL-2 on the Treg: Tcon ratio has not been studied in humans and correlative studies will be performed on all patients enrolled on this protocol to evaluate effect of combination therapy on normalizing immune reconstitution post-HCT in patients with steroid refractory cGVHD.

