#### 5.2 Treatment Schedule

##### 5.2.1 IL-2 Therapy

D. IL-2 will be self-administered by patients as a daily subcutaneous injection. Teaching will be provided before the first subcutaneous injection. The pharmacist, or the primary pharmacy technician working under the supervision of the pharmacist, will prepare the drug under aseptic conditions. The amount (in IU) of drug to be administered will be determined based on body surface area (BSA). The dose should be calculated based on body weight at screening, at a dose of  $1 \times 10^6$  IU/m^2/day for 12 weeks. All treatments will be outpatient based. If however, patients live within a 15 mile distance of the medical center and /or insurance mandates that the IL-2 be given in physician office- IL-2 injections will be given in the infusion center. After completion of 12 weeks of protocol therapy, responding patients will have the option of continuation of therapy till clinical benefit is no longer maintained. IL-2 will be provided by Prometheus Labs for this study. No protocol specific monitoring or follow up data will be collected after initial 12 week period. Monitoring of these patients will be according to acceptable standards of care for patients on cytokine therapy with IL-2. Ongoing responses will be monitored by the NIH consensus criteria guidelines , again off protocol . We hypothesize that maintenance therapy with IL-2 and ECP will

maintain elevated T reg: Tcon ratio, thereby translating into fewer clinical relapses and improved clinical outcomes.

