### **5.3 Planned Duration of Therapy:**

IL-2 and ECP combination therapy will be given for 12 weeks, with final immune assessment occurring at 16 weeks post-initiation of therapy. Patients deemed to be benefiting from combination therapy (i.e. in complete remission, partial remission, minor response or stable disease), will have the options to continue onto the extended duration per discretion of treating physician.

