## 5.8 Additional Studies:

Baseline evaluations, tests or exams are valid 3 weeks prior to the start of treatment.

At baseline, weeks 3, 7, 9, 12 and 16, an additional 30ml of whole blood will be collected in EDTA tube (lavender top) for flow cytometry of immune cell subsets and 5 ml in serum separator tube (yellow top) for cytokine analysis.

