3) Study miRNA expression in Tcon with or without Treg suppression: Experimental approach: Peripheral blood mononuclear cell (PBMC's) from all enrolled patients will be extracted from whole blood using Ficoll paque density gradient centrifugation (GE healthcare) at baseline. The PBMC's will then be flow sorted into 95% pure population of Tregs (CD4+CD25+CD127-) and Tcons (CD4+CD25+CD127-) using FACSaria cell sorter (BD Biosciences). Co-culture of Tregs and Tcons will be done in 96 well round bottom plates (Corning star, Cambridge, MA). Cells will be plated at

density of  $1 \times 10^5$ /cells/well in RPMI 1640 media (0.2mL/well) and incubated at 37C for 72 hours. Cultures will be stimulated by 1 $\mu$ gm/mL anti-CD3 antibody (BD PharMingen, San Diego, CA). miRNA expression of Treg suppressed and Treg unsuppressed Tcons will be investigated by miRCURY LNA™ microRNA Array (Exiqon, Vedbaek, Denmark). The intensity of signal will be calculated after background subtraction. The threshold value to screen up or down regulation of miRNAs will be a fold change  $\geq 2.0$  or  $\leq 0.5$ . Analysis Plan: The specific time trend for each cell subset, cytokine and miR will be assessed using linear mixed effects modeling. The overall fit of the model will be evaluated graphically by taking a scatter plot of data for each and applying an overlay of the line generated by the model. An evaluation of the regulation patterns over time will be assessed by examining the slope patterns. To assess the possible impact of changes in expression on T cells, functional regression modeling will be used. Similar modeling techniques will be used to assess the impact of clinical events on expression.

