**Immune Assessment:**

Patients will undergo testing for immunologic function, performed at baseline and at weeks 3, 7, 9, 12 and 16 (or 4 weeks after end of treatment). Testing will include: quantitative immune globulins; plasma banking; and storage of additional mononuclear cells.

**ECP Performance Parameters:** Clinical Response to therapy will be co-related with ECP performance parameters which will include median time spent on ECP machine, second versus third generation device ( Cellex vs XTS) and flow rates.

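### The week-16 immune sample is labelled as four weeks off therapy, but patients who benefit may still be receiving IL-2 and ECP at that visit

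*Combined protocol and SAP*

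**What the plan says.** **Timing of the last sample.** Section 9.1 schedules cell-subset analyses at baseline, at weeks 3, 7, 9 and 12, and then "4 weeks after discontinuation of combination therapy (week 16 for those who complete treatment". Section 11.2 (Immune Assessment) pairs the two in the same way: testing is "performed at baseline and at weeks 3, 7, 9, 12 and 16 (or 4 weeks after end of treatment". Section 5.3 gives 12 weeks of treatment "with final immune assessment occurring at 16 weeks post-initiation of therapy". Section 5.8 also names a fixed week: "At baseline, weeks 3, 7, 9, 12 and 16, an additional 30ml of whole blood will be collected".

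**Treatment after week 12.** Section 5.2.1 states that "responding patients will have the option of continuation of therapy till clinical benefit is no longer maintained". Section 5.3 opens this to patients in complete or partial remission, with minor response or with stable disease, at the physician's discretion. Section 5.4 describes the same combination of daily IL-2 and ECP, and item C of Section 2.1.4 has responders going on with both. Section 5.2.1 and item C add that no protocol-specific follow-up data are collected beyond the 12 weeks.

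**Expected immune behaviour.** Section 2.1.4 reports that the Treg expansion "declined to baseline levels 4 weeks after discontinuation of subcutaneous IL-2". Its item C hypothesises that maintenance keeps the Treg:Tcon ratio raised.

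**Analysis.** Section 2.1.5 aims to correlate clinical response with changes in immune subsets. Section 9.2.2 says: "The specific time trend for each cell subset, cytokine and miR will be assessed using linear mixed effects modeling", with similar models for clinical events. Neither Section 9.2.2 nor Section 13.2 mentions treatment status or says how week 16 is used.

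**The concern.** The label is right for a patient who completes 12 weeks and stops. It is wrong for one who completes 12 weeks and carries on. Whether a patient may carry on depends on response at week 12, so on/off status at week 16 is tied to the variable with which the immune data are to be correlated.

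An immune difference between responders and non-responders at week 16, or a difference in slope driven by that visit, could then reflect who was still being treated rather than any link between Tregs and response. A pooled time trend would also blend a washout with continued treatment. If status is not recorded, this may not be separable afterwards.

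**Working it through.** **1. The plan's own figure.** The plan gives no sample size or power for the immune analyses. Its only sized design is the Simon two-stage design in Section 13.1, which fixes N = 24. The chance of rejecting is the sum over x = 3 to 9 of P(Bin(9, p) = x) × P(Bin(15, p) ≥ 10 − x). This gives 0.0485 at p = 0.25 and 0.8055 at p = 0.50, matching the stated 0.05 and 0.80. That design is not in question; only N = 24 is carried forward.

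**2. Status at week 16 under a fixed visit, for patients who complete 12 weeks.**

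| Patient | Status at week 16 | Label in 9.1 | Expected (2.1.4) |
|---|---|---|---|
| Benefiting, continues | On therapy | 4 weeks off | Treg:Tcon still raised |
| Benefiting, stops | 4 weeks off | 4 weeks off | Tregs at baseline |
| Not benefiting, stops | 4 weeks off | 4 weeks off | Tregs at baseline |

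Only the first row is mislabelled, and it contains only patients judged to be benefiting.

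**3. Inputs for an illustration.** Section 2.1.3 gives phase I medians on IL-2: Treg count more than 8 times baseline (peak, week 4) and Treg:Tcon ratio more than 5 times baseline. I take an on-therapy fold F = 5 and F = 8.

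Assumptions, not in the documents: F is constant from week 3 while on therapy; the fold is 1 at four weeks off; responders and non-responders do not differ while on therapy; only responders continue.

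**4. Week-16 level.** If a share q of a group is still on therapy, its mean log fold is q × ln F, so the geometric mean fold is F^q.

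| q | F = 5 | F = 8 |
|---|---|---|
| 0 | 1.00 | 1.00 |
| 0.50 | 2.24 | 2.83 |
| 0.75 | 3.34 | 4.76 |
| 1 | 5.00 | 8.00 |

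Non-responders are at 1.00, so with q as the share of responders continuing, these are also the responder to non-responder ratios at week 16 with no true association.

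**5. Linear slope.** The visits 0, 3, 7, 9, 12 and 16 have mean 47/6 = 7.833 and sum of squared deviations 170.83. Week 16 deviates by 8.167. The slope difference if all responders continue is ln F × 8.167 / 170.83:
- F = 5: 1.609 × 8.167 / 170.83 = 0.077 log units per week.
- F = 8: 2.079 × 8.167 / 170.83 = 0.099 log units per week.

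For a whole group, the slope moves from about zero (−0.003 to −0.004) with nobody on therapy at week 16 to 0.074–0.095 with everyone on.

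**6. False-positive rate.** Simulation with 4,000 runs, N = 24, each patient a responder with probability 0.5, between-patient log SD 0.5, within-patient log SD 0.5 or 1.0, and a two-sided 5% t-test comparing per-patient slopes:

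| Share of responders continuing | Week 16 included, status ignored | Trend ended at week 12 |
|---|---|---|
| 0 | 0.05 | 0.04–0.06 |
| 0.5 | 0.20–0.58 | 0.05 |
| 1 | 0.63–1.00 | 0.05–0.06 |

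The t-test on slopes stands in for a model that Section 9.2.2 does not specify in detail.

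**The case against.** **The main immune results avoid week 16.** The primary immunologic endpoint in Section 9.1 is set at 3 months of therapy. The one explicit responder versus non-responder immune test, for plasma microRNA in Section 9.2.2, uses samples from baseline and week 12. This stands and limits the scope.

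**The plan does not say that the models include week 16.** Section 9.2.2 lists no time points, and no week-16 responder test is written. This also stands. The exposure arises because week 16 is on the sampling schedule and nothing excludes it or conditions on status.

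**Continuers might be sampled later or not at all.** Sections 9.1 and 11.2 mention four weeks after treatment ends, and Section 5.2.1 says that no follow-up data are collected after week 12. The problem would then be shifted or missing data. Sections 5.3 and 5.8 favour a fixed week 16, but the text is not consistent. Under this reading too, availability or timing of the last sample depends on response.

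**The split may not be clean.** Continuation is optional, Sections 2.1.4 and 5.4 refer to commercial IL-2, and Section 14.6 reports an insurance coverage rate of 60%. Section 13.1 counts stable disease as response, while Section 13.2 gives CR+PR; under the latter, some non-responders could also continue. These points reduce the size of any artefact but do not remove it.

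**The fold figures are loose.** The 8-fold value is a week-4 peak median from a phase I study, and no week-16 value on continued therapy is given. It is an illustration, not a bound.

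**Conclusion.** The concern holds in a limited form. The equation of week 16 with four weeks off therapy is wrong for any completer who continues and is sampled at week 16. An analysis of response or time trend that uses that visit without treatment status could mistake continued treatment for an immune correlate of response. Under the assumptions above, the artefact is nil if nobody continues, about 2.2- to 2.8-fold if half of responders continue, and about 5- to 8-fold if all responders and only they continue.

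Stronger readings that the documents do not support:
- A reader might infer that the trial's central question is compromised. The trial is designed and sized for clinical response; immunologic effects are one secondary objective, and the 3-month immunologic endpoint is untouched.
- A reader might infer that responders will mostly be on drug at week 16. No share is given.
- A reader might infer from Section 2.1.2 that nobody is off ECP at week 16. It describes one month plus three months of ECP and says: "For the purpose of this trial, we will continue using this regimen based on extensive local experience". Taking three months as 13 weeks, that is 8 + 13 = 21 procedures over about 17 weeks, against 8 + 8 = 16 ending in week 11 in Section 5.2.2. The two sections must be reconciled, but this is a separate matter and the point here does not rest on it.

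**What to change.** 1. Record at week 16 whether the patient is receiving IL-2 and ECP, with the date of the last dose of each.
2. State in Section 9.2.2 or 13.2 that the main longitudinal and response-correlation models use baseline to week 12. Alternatively, keep week 16 and include on/off therapy as a time-varying term.
3. Report week 16 descriptively by treatment status, with no responder versus non-responder comparison that ignores status.
4. Correct the week-16 label in Sections 9.1 and 11.2; the steroid-use record in 11.2 carries the same label. Reconcile Sections 2.1.4 (item C) and 5.2.1, which end data collection at week 12, with 5.3, 5.8, 9.1 and 11.2, which schedule a week-16 sample. Say whether continuing patients are sampled at week 16.
5. Separately, reconcile the ECP durations in Sections 2.1.2 and 5.2.2.

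The cost is a small addition to the week-16 form and a few sentences. Under the first option in item 2, week 16 leaves the main trend; the time-varying term keeps the washout data but adds a parameter to a model fitted to at most 24 patients. Item 1 should be in place before week-16 visits take place, because status that is not recorded may not be recoverable.
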